12.1 CRITERIA FOR THERAPEUTIC RESPONSE/OUTCOME ASSESSMENT

Response will be determined by the MDS International Working Group criteria (47).

12.2 Complete Remission (CR)

Bone marrow evaluation: Repeat bone marrow showing 5% or less myeloblasts with

**Memorial Sloan Kettering Cancer Center
[name]
[name]**

normal maturation of all cell lines. Persistent dysplasia will be noted. (*)

Peripheral Blood: Absolute values must last at least 1 months. In some circumstances, protocol therapy may require the initiation of further treatment before the 1 month period. Such patients can be included in the response criteria into which they fit at the time therapy is started. Transient cytopenias during repeated chemotherapy courses should not be considered as interrupting durability of response, as long as they recover to the improved counts of the previous course.

Hgb \geq 11 g/dL (untransfused, patient not on erythropoietin)
Neutrophils \geq 1500/mm³ or more (not on myeloid growth factor)
Platelets \geq 100,000/mm³ or more (not on thrombopoietic factor)
Blasts 0%

(*) Dysplastic changes should consider the normal range of dysplastic changes (modification).

12.3 Partial Remission (PR)

Absolute values must last at least 1 months unless interrupted by therapy as described above.

All the CR criteria (if abnormal before treatment) except:

Bone marrow evaluation: Blasts decreased by 50% or more over pretreatment, but still more than 5 %. Cellularity and morphology are not relevant

12.3 Marrow CR

Bone Marrow: 5% myeloblasts or less and decrease by 50 % or greater over pretreatment.

Peripheral Blood: if HI responses, they will be noted in addition to marrow CR

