6.1 CRITERIA FOR SUBJECT ELIGIBILITY

6.2 Subject Inclusion Criteria

- Diagnosis of a myelodysplastic syndrome according to the FAB classification system, which has been confirmed at MSKCC
- Age greater than or equal to 18 years
- IPSS score of greater than or equal to 0.5.
- Performance Status of ≥ 60 % (Karnofsky)
- Serum total bilirubin ≤ 2.5
- SGOT and SGPT should be ≤ 2 times the upper limit of normal.
- Serum creatinine should be $\leq 1.5 \times$ ULN, or 24 hour creatinine clearance must be ≥ 60 cc/min.
- Negative pregnancy test for women with child-bearing potential.
- Female patients with child-bearing potential or male patients who are sexually active must agree to use an accepted form of contraception.
- Signed informed consent
- Transplant ineligible prior to therapy
- Prior 5-azacytidine recipients are eligible regardless of prior response to 5-azacytidine.
- Prior decitabine recipients must have had a response (HI or better per IWG Response Criteria), followed by POD (POD after decitabine was discontinued).
- Patients will be eligible for entry if they have IPSS Intermediate-1, Intermediate-2 or High Risk disease.

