Once the MTD is established, patients will be accrued to the phase II portion of the study which will evaluate the efficacy of decitabine in combination with the MTD of tretinoin. The phase II study will have a 2-stage design. In the first stage of this design, twenty seven patients will be treated. Patients treated at the tretinoin MTD (6 patients) in the phase I portion of the study will be carried over and counted among the patients in stage 1. If two or fewer responses (CR or PR) are seen among the first 27 patients, the study will be closed for lack of efficacy. If at least three responses (CR or PR) are seen in the first stage, then an additional 13 patients will be accrued in the second stage. To qualify as a non-responder, patients must undergo disease re-evaluation studies (bone marrow and complete blood counts) after completing four cycles of therapy.

Treatment will be recycled every 28 days, provided there is adequate recovery from non-hematologic toxicities. The start of cycle #1, or subsequent cycles may be delayed for up to 2 weeks in the event of 1) uncontrolled infection, or 2) other abnormalities that would preclude patient eligibility (see sections 6.1 and 6.2).

Patients will receive treatment for a minimum of 4 cycles, barring removal for progression of disease or excessive toxicity. Patients must achieve hematologic improvement (HI) or Bone Marrow PR/CR by the completion of cycle #6. Patients achieving HI or bone marrow PR/CR by the completion of cycle #6 may receive up to a total of 10 cycles of therapy, barring excessive toxicity. If the best response after cycle #6 is Stable Disease, these patients will be removed from study. Patients in the phase I study will continue at the study entry dose. Treatment will be interrupted for grade III or IV non-hematologic toxicity attributable to tretinoin or decitabine. Therapy may be resumed with the next cycle of treatment as long as the toxicity has decreased to < grade 2 within 8 weeks of the last treatment administration. However, these patients will receive a 25% dose reduction in tretinoin or decitabine (which ever treatment is suspected or both if the attribution is unknown) when treatment resumes. All patients will be followed for Serious Adverse Events (SAEs) for 30 days after completion of the last cycle of therapy (each cycle is 28 days).

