10.1 EVALUATION DURING TREATMENT

10.2 Safety Monitoring:

Weekly while on study: Complete blood count (including differential)

Within 7 days of starting each cycle: CBC, Comprehensive metabolic panel, pregnancy test for patients with child-bearing potential, physical exam, assessment of performance status, medications and adverse events. Patients will be asked to maintain a symptom diary each cycle, which will be reviewed prior to starting each subsequent cycle. Patients will keep a tretinoin administration log, which will be reviewed with the patient. A pill count will be performed and correlated with the patient's tretinoin administration log to assess compliance with tretinoin administration. Physical exam and toxicity assessments may be required more frequently if clinically indicated.

10.3 Tests for Disease Response:

Complete blood count with differential and smear review prior to start of all treatment cycles.

Bone marrow aspirate and biopsy after even-numbered cycles (eg., 2, 4, 6, etc). Bone marrow aspirate studies for disease assessments will include flow cytometry, cytogenetics, and histochemistry.

10.4 Research Samples:

Research samples will be obtained on patients treated in the phase I and the phase II portion of this study at the following time points:

- (1) Prior to treatment (during the screening period when screening baseline bone marrow and bloodwork is obtained), blood (30 cc in heparin) and bone marrow aspirate (10 cc in heparin) will be obtained.
- (2) During cycle #1 and cycle # 2, on days 10 and 19, blood (30 cc in heparin) will be obtained for research purposes only (blood to be drawn with weekly routine blood work).
- (3) During cycle #1 only, on days 10 and 19, bone marrow aspirate (10 cc in heparin) will be taken for research purposes only.
- (4) At the time of scheduled disease assessments done after cycles 2 and 4, blood (30 cc in heparin) and bone marrow aspirate (10 cc in heparin) will be obtained.

10.5 Research Tests:

The following research studies will be performed at the time points indicated in 10.3 when feasible:

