12.6 Relapse after CR or PR

One or more of the following:

- a) Return to pretreatment bone marrow blast percentage
- b) Decrement of 50% or greater from maximum remission / response levels in granulocytes or platelets
- c) Reduction in hemoglobin concentration by at least 1.5 g/dL or new/recurrent transfusion dependence (in the absence of another explanation such as treatment effect, acute infection, gastrointestinal bleeding, hemolysis and so on)

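### Marrow CR and blast relapse 12.6(a) have no blast floor, so in patients who enter at 5% blasts or less both can be scored on counting error (minor: scoring and reporting only)

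*Combined protocol and SAP*

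**What the plan says.** Marrow CR (the second of the two sections numbered 12.3) has one marrow condition: "Bone Marrow: 5% myeloblasts or less and decrease by 50 % or greater over pretreatment". Hematologic improvement is noted alongside if present. No pretreatment minimum or smallest absolute change is given.

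Entry requires "IPSS score of greater than or equal to 0.5" (Section 6.2). Appendix I gives 0 points for blasts under 5%, and two or three cytopenias alone supply 0.5. Appendix II includes two FAB subtypes, RA and RARS, with marrow blasts under 5%. Patients at or below 5% are therefore eligible.

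Section 12.6 defines relapse after CR or PR as "One or more of the following", and item (a) is "Return to pretreatment bone marrow blast percentage". CR itself (Section 12.2) allows blasts up to the same limit: "Repeat bone marrow showing 5% or less myeloblasts with" normal maturation, plus blood-count conditions.

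Disease assessment (Section 10.3) is "Bone marrow aspirate and biopsy after even-numbered cycles (eg., 2, 4, 6, etc", which gives three marrows by the end of cycle 6.

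**The concern.** A patient who enters at 2% or 3% blasts meets the 5% limit of marrow CR before any drug is given. Only the relative fall remains to be met, and at such low percentages a halving is a difference of a few cells on the slide. With three marrows by cycle 6 there are three chances to record one.

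The neighbouring rules are protected. PR requires "Blasts decreased by 50% or more over pretreatment, but still more than 5" percent, which can happen only if pretreatment blasts exceeded 10%. Progression item 12.7(a) requires a rise to above 5%. Marrow CR and 12.6(a) have no equivalent, which looks like an omission.

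At stake is what a marrow CR or a blast relapse would mean if either is tabulated. In a single-arm trial no control group would show how many such events arise without any drug effect.

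**Working it through.** **The plan's own figure.** The only related calculation in the plan is the two-stage design in Section 14.1: 27 then 13 patients, at least 3 responses to continue, at least 7 of 40 for a positive result. The probability of a positive result is the sum over x = 3 to 27 of P(X1 = x) × P(X2 ≥ 7 − x), with X1 ~ Bin(27, p) and X2 ~ Bin(13, p). This gives 0.0977 at p = 10% and 0.9001 at p = 25%, matching the stated error rates of 0.10 and 0.10. Marrow CR is not a response in this rule, so nothing below changes these figures.

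**Direct reading.** Pretreatment 2%, later 1%: at or below 5%, and a 50% fall, so marrow CR. Pretreatment 3%, CR at 1%, later 3%: 12.6(a) is met although 3% is within CR's 5% limit. At a pretreatment value of 0%, a 50% fall is undefined.

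**Counting-error model for marrow CR.** Hold the true blast fraction p constant. The pretreatment count X and each later count are independent Bin(m, p). The documents do not give the number of cells counted, so m = 200 and m = 500 are assumed. Let f(x) = P(X = x) and let F(x) be the probability that a later count is at most x/2 and at most 5% of m, with F(0) = 0.

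- One marrow: Σ f(x) F(x)
- At least one of three marrows: Σ f(x) [1 − (1 − F(x))³]

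Example at m = 200, p = 2%: for x = 4 (a 2% reading), f = 0.1973 and F = P(count ≤ 2) = 0.2351, so the bracket is 1 − 0.7649³ = 0.5525. For x = 6, f = 0.1047, F = 0.4315 and the bracket is 0.816. Summing over all x gives 0.465.

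| True blasts | One marrow, 200 / 500 cells | Any of three, 200 / 500 cells | Any of three with recorded pretreatment >5%, 200 / 500 cells |
|---|---|---|---|
| 1% | 31.9% / 18.3% | 59.0% / 40.5% | 0.0% / 0.0% |
| 2% | 21.8% / 8.2% | 46.5% / 20.5% | 0.3% / 0.0% |
| 3% | 15.2% / 4.0% | 34.9% / 10.6% | 3.5% / 0.4% |
| 4% | 10.9% / 2.0% | 26.3% / 5.4% | 11.1% / 2.7% |

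The last column does not reach zero because some pretreatment readings exceed 5% by chance.

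**Same model for 12.6(a).** A return implies an earlier fall, so three readings are needed: pretreatment X at or below 5%, an earlier follow-up Y below X, and a later Z at or above X but still at or below 5%. The rate is P(all three conditions) divided by P(X ≤ 5% and Y < X).

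- 200 cells: 0.158 / 0.425 ≈ 0.37 at a true 2%; 0.144 / 0.402 ≈ 0.36 at 3%
- 500 cells: 0.164 / 0.455 ≈ 0.36 at 2%; 0.162 / 0.457 ≈ 0.35 at 3%

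So a little over a third of unchanged patients with an earlier lower reading meet 12.6(a) at the later marrow. The blood-count and maturation conditions of CR are not modelled.

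**The case against.** The strongest answer is that no planned result uses either category. The phase II response is CR or PR. Section 14.1 lists hematologic improvement, transfusions, bleeding, infections and laboratory correlates, but no marrow CR rate, relapse rate or response duration. Secondary endpoint 1 mentions marrow morphology without naming marrow CR. This stands, and it limits the point to a minor one.

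A reader might infer that counting error decides who is treated beyond cycle 6, because Section 9.0 says "Patients achieving HI or bone marrow PR/CR by the completion of cycle #6 may receive up to a total of 10 cycles of therapy". The documents do not establish that. The marrow-response term there is undefined. Section 12.4 classes anything short of a PR as stable disease, Section 9.0 removes patients whose best response after cycle 6 is stable disease, and Section 13.2 removes those without at least a PR after six cycles. On those passages a marrow CR alone would not keep a patient on study. That is a conflict between sections, separate from the missing floor.

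A reader might also infer that CR and relapse hold on the same marrow when a patient enters at 3% and reaches CR at 3%. Returning implies having left, so that reading is strained. Ignoring the need for an earlier fall would put the 12.6(a) rate at 52–57% for true blasts of 2–3%, which overstates it.

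Nor do the documents support calling a marrow CR rate mostly noise. They give neither the true marrow response rate in low-blast patients nor the share of patients who will enter at 5% or less.

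Two smaller objections have some force. The lack of a confirmatory marrow is not special to marrow CR, since CR's one-month rule attaches to blood values. Section 12.1 adopts published working-group criteria that cannot be consulted here, so whether a floor departs from them cannot be judged. Section 12 nonetheless writes out its own definitions, and these contain no floor.

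**Conclusion.** The gap is in the text and holds for both rules. As written, an eligible patient at 5% blasts or less can be scored a marrow CR on a trivial relative change. A CR patient who entered at that level can meet 12.6(a) without leaving CR's blast range. The 12.6(a) problem concerns CR patients only, since PR requires pretreatment blasts above 10%.

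The size depends strongly on the number of cells counted: across true blasts of 1–4%, the three-marrow false rate runs from 59.0% down to 5.4%. The model assumes constant true blasts, independent counts and sampling error alone; differences between readers and aspirates would add to it. How many of the 40 patients would be affected cannot be stated from the documents.

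The primary endpoint and its error rates are unaffected and no planned analysis depends on these categories. Severity is minor: a correction to how the categories are scored and reported.

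**What to change.** For scoring and reporting only:

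- **Marrow CR:** count it only in patients with pretreatment marrow blasts above 5%, and report the rate with those patients as the denominator.
- **12.6(a):** score a return to the pretreatment blast percentage as relapse only when blasts are also above 5%.

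This costs two lines in Section 12, with no added procedures or patients. The downside is a smaller marrow CR denominator, which also leaves out a patient at exactly 5%, where Appendix II starts RAEB. Patients at 5% or less remain assessable for CR and hematologic improvement. The floor reduces false marrow CRs but does not remove them when true blasts lie close to 5%.

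Separately, the cycle 6 wording in Sections 1.0 and 9.0, which accepts hematologic improvement or a marrow response, conflicts with the at-least-PR wording in Sections 12.4 and 13.2. These passages must be reconciled. No continuation rule is proposed here.

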12.4 Stable Disease

Failure to achieve at least a PR, but with no evidence of progression for at least 2 months

12.5 Failure

Death during treatment or disease progression characterized by worsening of cytopenias, increase in the percentage of bone marrow blasts, or progression to an MDS FAB subtype more advanced than pretreatment. Progression to AML (30% or more bone marrow blasts)

12.6 Relapse after CR or PR

One or more of the following:

- a) Return to pretreatment bone marrow blast percentage
- b) Decrement of 50% or greater from maximum remission / response levels in granulocytes or platelets
- c) Reduction in hemoglobin concentration by at least 1.5 g/dL or new/recurrent transfusion dependence (in the absence of another explanation such as treatment effect, acute infection, gastrointestinal bleeding, hemolysis and so on)

12.7 Disease Progression

- a) For patient with less than 5% blasts: a 50% or more increase in blasts to more than 5% blasts
- b) For patients with 5% to 10% blasts: a 50% or more increase to more than 10% blasts.
- c) For patients with 10% to 20% blasts: a 50% or more increase to more than 20% blasts
- d) For patients with 20% to 30% blasts: a 50% or more increase to more than 30% blasts.
- e) One or more of the following: 50% or greater decrement from maximum remission/response levels in granulocytes or platelets, reduction in hemoglobin concentration by at least 2 g/dL, or transfusion dependence (in absence of another explanation such as acute infection, G.I. bleeding, hemolysis etc.)

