8.1 PRETREATMENT EVALUATION

8.2 Pre-study Evaluation (Eligibility Assessment)

Eligibility evaluations to be performed within 30 days of starting therapy with decitabine and tretinoin will include the following:

- Bone marrow aspirate for histology, cytogenetics, flow cytometry, and a bone marrow biopsy.
- Baseline bone marrow aspirate will also be obtained for research studies. Therefore patients will be consented prior to their baseline bone marrow procedure.
- Physical exam with review of systems, medical history, Karnofsky performance status, , FAB classification, history of prior medications, prior MDS treatments, history of transfusions requirements for two months prior to registration.
- Determination of elements of IPSS (bone marrow aspirate and complete blood count), which produces IPSS score of 0.5 or greater.
- Electrocardiogram (EKG)
- Comprehensive metabolic panel, CBC with differential and smear review, reticulocyte count, pregnancy test for women with child-bearing potential.
- Assessment of ability of the patient to comply with the requirements of the protocol.

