12.8 Hematologic Improvement (HI)

Improvements must last at least 2 months in the absence of ongoing cytotoxic therapy. When protocol therapy requires the initiation of further treatment before the 2 month period, patients can be included in the response criteria into which they fit at the time therapy is started.

Hematologic improvement should be described by the number of individual, positively affected cell lines (eg, HI-E; HI-E + HI-N; HI-E + HI-P + HI-N).

1. Erythroid response (HI-E)

For patients with pretreatment hemoglobin less than 11g/dL: greater than 1.5 g/dL increase in hemoglobin, relevant reduction of units of RBC transfusions by an absolute number of at least 4 RBC/8wk compared with the pretreatment transfusion number in the previous 8 wk. (*)

(*) Only RBC transfusions given for Hgb > 9.0 g/dL pretreatment will count in the RBC transfusion response evaluation.

2. Platelet response (HI-P)

Memorial Sloan Kettering Cancer Center
[name]
[name]

For patients with a pretreatment platelet count less than 100 000/mm³: an absolute increase of 30 000/mm³ or more for patients starting with more than 20 000/mm³ platelets, an increase from less than 20 000/mm³ to greater than 20 000/mm³, and by at least 100%.

3. Neutrophil response (HI-N)

For patients with pretreatment neutrophil count less than 1 000/mm³: at least a 100% increase and an absolute increase of more than 500mm³.

4. Progression/relapse after HI

One or more of the following: A 50% or greater decrement from maximum response levels in granulocytes or platelets, a reduction in hemoglobin concentration by at least 1.5 g/dL, or transfusion dependence (in the absence of other explanation, such as hemolysis, hemorrhage, etc).

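### Section 12.7(e) counts transfusion dependence as disease progression without requiring it to be new, recurrent or worse than before treatment

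*Combined protocol and SAP*

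**What the plan says.** Section 12.7 lists five routes to disease progression. Route (e) is met by any one of three findings: a fall of half or more in granulocytes or platelets from their best level, a hemoglobin fall of at least 2 g/dL, "or transfusion dependence (in absence of another explanation such as acute infection, G.I. bleeding, hemolysis etc".

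Three other rules deal with transfusion need:

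- Section 12.6(c), relapse after CR or PR: "new/recurrent transfusion dependence (in the absence of another explanation such as treatment effect, acute infection".
- Section 12.8(1), erythroid improvement (HI-E): "reduction of units of RBC transfusions by an absolute number of at least 4 RBC/8wk compared with the pretreatment transfusion number" over the previous 8 weeks. Its footnote, as printed, counts only red-cell transfusions given at a pretreatment hemoglobin above 9.0 g/dL.
- Section 12.8(4), progression or relapse after HI: "or transfusion dependence (in the absence of other explanation, such as hemolysis, hemorrhage, etc".

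Neither the inclusion criteria (6.2) nor the exclusion criteria (6.3) bar transfused patients. Section 8.2 collects a "history of transfusions requirements for two months prior to registration".

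Section 13.1 removes patients with progressive disease and points to Section 12 for the definition. Section 9.0 sets a minimum of four cycles, with progression as one of the exceptions.

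**The concern.** Everything else in 12.7 describes a change. Transfusion dependence in 12.7(e) describes a condition that a patient may already have on the day of registration. The protocol gives it no baseline, no unit count and no time window. Section 12.6(c) contains the kind of qualifier that is missing, so the omission is visible within the same section.

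What is at stake is classification and time on treatment. A patient whose transfusion need has not moved could be recorded as progressed when Stable Disease is correct, because 12.4 requires that progression be absent. The same patient could be taken off study before the assessment that Section 9.0 relies on: "To qualify as a non-responder, patients must undergo disease re-evaluation studies (bone marrow and complete blood counts) after completing four cycles of therapy". A patient with hematologic improvement might also be pulled in two directions, since Section 9.0 states that "Patients achieving HI or bone marrow PR/CR by the completion of cycle #6 may receive up to a total of 10 cycles of therapy" while 13.1 removes anyone who has progressed.

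**Working it through.** **1. The rules side by side.**

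| Rule | What the finding is compared with |
|---|---|
| 12.7(a)–(d), blasts | Starting blast range; a rise of at least half past a stated limit |
| 12.7(e), granulocytes or platelets | Best level reached |
| 12.7(e), hemoglobin | A fall of at least 2 g/dL |
| 12.7(e), transfusion dependence | Nothing |
| 12.6(c), transfusion dependence | Must be new or recurrent |
| 12.8(1), HI-E transfusions | Pretreatment 8-week number |
| 12.8(4), transfusion dependence | Nothing |

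**2. The unchanged patient.** Let U be units per 8 weeks before treatment, V units per 8 weeks on treatment, and T the number per 8 weeks that counts as dependence. The documents do not give T; I assume 1, 2 or 4. As written, 12.7(e) is met when V ≥ T. With no change V = U, so it is met whenever U ≥ T. A patient at 8 units before and 8 units on treatment meets it for each assumed T. This result does not use the HI-E rule at all.

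**3. When removal could fall.** Take 28-day cycles with no delays. Under Section 10.3, marrow is examined on this schedule: "Bone marrow aspirate and biopsy after even-numbered cycles". The first such marrow follows cycle 2, at 2 × 28 = day 56, which is 8 weeks. The four-cycle re-evaluation is at 4 × 28 = day 112.

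- If dependence is judged over less than 8 weeks, removal could precede the day-56 marrow.
- If it is judged over 8 weeks, as HI-E does, the call falls at about day 56.
- Either way it can come before day 112.

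**4. The patient with HI-E.** Assume that the comma between the two limbs of HI-E means *or*, and that all on-treatment units count. The transfusion limb needs a cut of at least 4, so V ≤ U − 4. Meeting 12.7(e) as well needs V ≥ T. Both can hold only if U ≥ T + 4, that is U ≥ 5, 6 or 8 for T = 1, 2 or 4.

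This condition is necessary but not sufficient. Under the footnote, the count that must fall by 4 may be smaller than U. A cut from 8 units to 4 meets HI-E only if enough of the pretreatment units were given above 9.0 g/dL. Where the overlap does occur, the patient meets 12.8(4) too, because it uses the same unqualified term. So 12.8(4) is not a problem only for patients with neutrophil or platelet improvement.

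**5. The primary endpoint.** The plan attaches no figure to 12.7(e). The related figures are those of the phase II design in Section 14.1: 27 patients, continue with 3 or more responses, add 13, positive with 7 or more of 40. The probability of a positive result is the sum over x = 3 to 27 of P(X₁ = x) · P(X₂ ≥ 7 − x), with X₁ ~ Bin(27, p) and X₂ ~ Bin(13, p). It is 0.0977 at p = 0.10 and 0.9001 at p = 0.25, which agrees with the stated 0.10 and 0.90.

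CR requires an untransfused hemoglobin of at least 11 g/dL, and PR carries that over when the value was abnormal before treatment. Continuing red-cell dependence therefore does not reclassify a patient already in such a response. The only route to the response rate is removal before CR or PR is documented. The documents give neither the share of patients dependent at entry nor the share of responses that would be lost this way.

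**The case against.** The strongest reply is that nobody would apply the rule literally. The section is headed as progression, its other items are all changes, and 12.5 speaks of cytopenias getting worse. Taken literally, a dependent patient would have progressed on day 1 of a trial that plainly admits such patients. This is good evidence of intent, and it is why the point is minor. It does not amend the rule: 13.1 refers to the Section 12 definitions, and the definition that operates omits a qualifier supplied in 12.6(c).

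A second reply is that the clause on other explanations covers the case. Its list is open, so it already allows a drug effect. But dependence caused by the MDS is the disease itself and not another explanation.

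A third is that 12.1 adopts the International Working Group criteria. Whether the wording of 12.7(e) is theirs cannot be checked from the documents. If it is, the edit should be recorded as a protocol clarification.

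A fourth is that the consequences are thin, and this largely stands. Section 14.1 names no analysis of time to progression or of the Stable Disease rate. Section 9.0 only permits continued treatment after HI. Section 13.2 already conflicts with it after cycle 6 for patients with HI short of a PR, so 12.7(e) adds most before then.

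Two stronger readings are tempting. A reader might infer that HI-E responders who still need transfusions are necessarily scored as progressed. The text does not support that: it depends on the comma, the footnote and the undefined term, as shown in step 4. A reader might also infer a loss of power through early removals. Any such figure would need the two shares that the documents do not give.

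**Conclusion.** The point holds as a defect in one rule. As written, 12.7(e) scores a patient who was transfusion dependent at entry and is unchanged as having progressed. That patient loses Stable Disease and becomes removable before the four-cycle re-evaluation. The conclusion rests on the text alone and needs no assumed number beyond some threshold for dependence.

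The overlap with HI-E, and with it 12.8(4), is possible but conditional. No effect on power, type I error or response rate can be derived, and none is claimed. How many patients are affected is unknown. The documents do not show that any patient was misclassified, and an investigator who reads 12.7 together with 12.5 would probably avoid the error. Severity: minor.

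**What to change.** In 12.7(e), replace the bare term with: *new, recurrent or increased transfusion dependence compared with the pretreatment two-month history (or, after a response, compared with the best response level)*.

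In 12.8(4), write: *new or recurrent transfusion dependence, or an increase in transfusion need from the best response level*.

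Define dependence once, by a unit count over 8 weeks, and say how large an increase counts.

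The words *recurrent* and *best response level* are needed. A rule limited to new or increased need against pretreatment would miss a patient going from 8 units to 0 and back to 8, or from 8 to 4 and back to 8, although the erythroid response is lost in both. With the wording above, both are caught and a patient who stays at 8 is not.

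Naming treatment effect in 12.7(e), as 12.6(c) does, is optional because the open list already allows it. Section 13.1 needs no change.

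The cost is two phrases and a definition. The baseline comes from the history already collected under 8.2. No visits, tests or patients are added, and the sample size and error rates stay as they are.
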